7.8.1.8 COVID-19 related analyses

The subgroup of patients with SARS-COV-2 infection will be analysed. SARS-COV-2 infections will be defined by the narrow BIcMQ SARS-COV-2 infection. All analyses will be repeated using the broad instead of the narrow BIcMQ.

An overview of adverse events will be presented for this subgroup of patients. Additionally, the number of patients with adverse events, the number of serious AEs and AEs leading to discontinuation of study treatment will be presented by treatment, primary SOC and preferred term.

A listing will be prepared presenting all SARS-COV-2 infections.

7.8.2 **Laboratory data**

Standard safety tables will not include eGFR or creatinine. Analyses for eGFR and creatinine will be done separately.

For continuous safety laboratory parameters, normalised values will be derived, as well as the differences to baseline. The process of normalisation as well as standard analyses for safety laboratory data are described in the BI guidance for the Display and Analysis of Laboratory Data (9). All analyses considering multiples of upper limits of normal (ULN) will be based on original and not normalised data.

Laboratory parameters will be shown in conventional units. Where conventional units differ from SI units, analyses will be repeated on SI units.

Laboratory measurements (not mentioned in [Table 6.1: 2](#)) taken up to 3 days after the last administration of randomised study drug will be considered as on-treatment. Default settings will be used for repeated values (using closest and then worst value).

Laboratory values will be compared to their reference ranges and frequency tables will be provided for the number of patients within and outside the reference range at baseline and the last measurement on treatment. Descriptive statistics will be provided by treatment group for baseline, last value on-treatment and for changes from baseline to last value on treatment. For semi-quantitative or categorical laboratory values, shift tables for baseline and last value on treatment will also be provided. Frequency tables will summarise the number of patients with potentially clinically significant abnormalities.

Additionally, for urine ketones. a shift table of baseline vs value at each visit will be shown.

For the table of potentially clinically significant abnormalities, only patients with at least one available on-treatment value will be included in the analysis of an individual laboratory parameter. Other tables are comparing baseline to on-treatment values and will only include patients with a baseline value and at least one available on-treatment value. All individual data will be presented in listings.

To support analyses of liver-related adverse drug effects, patients with Aspartate transaminase (AST) and/or Alanine transaminase (ALT) $\geq 3 \times \text{ULN}$ with concomitant or subsequent Total Bilirubin (TBILI) $\geq 2 \times \text{ULN}$ in a 30 day period after AST/ALT elevation are of special interest. In addition, of these cases, it will be considered whether the alkaline phosphatase (AP) is less than $2 \times \text{ULN}$ (maximum value in a 30 day period after AST/ALT elevation) or not. The start of the 30-day time span is triggered by each liver enzyme elevation above the defined thresholds. Patients who fulfil one or two of the criteria for ALT/AST or total bilirubin elevations above and have no information available for the remaining parameter(s) within the 30 day time window will not be listed under “ALT and/or AST $\geq 3 \times \text{ULN}$ with TBILI $\geq 2 \times \text{ULN}$ ”.

In addition, ALT/AST will be used to investigate elevated liver enzymes:

- ALT/AST $\geq 3 \times \text{ULN}$
- ALT/AST $\geq 5 \times \text{ULN}$
- ALT/AST $\geq 10 \times \text{ULN}$
- ALT/AST $\geq 20 \times \text{ULN}$

All liver enzyme elevations within 30 days of treatment discontinuation will be shown.

Frequency tables of patients with elevated liver enzymes defined by ALT and/or AST, total bilirubin and AP combinations will be provided. Details on patients with elevated liver enzymes will be listed.

For the following parameters:

- eGFR,

- haemoglobin,
- haematocrit,
- creatinine (only descriptive),

the time course of changes will be assessed. The analysis will be performed by applying MMRM models to the TS (on-treatment data) and the RS (all data). No imputation will be applied. The MMRM models that will be used are specified in [Section 7.5.2](#). These analyses will be conducted on data before any normalisation. The MMRM analyses will also be shown graphically.

To support analysis of renal function, eGFR throughout the trial will be categorised according to the following Chronic Kidney Disease (CKD) staging ([Table 7.8.2: 1](#)): All calculations for the staging of renal function will be based on the originally measured laboratory values, not on normalised values with BI standard reference ranges.

Table 7.8.2: 1 CKD staging

Stage	eGFR (mL/min/1.73m ²)	Description	Label for displays	Additional labels
1	≥90	Normal or high	≥90	≥90 (CKD 1)
2	60 to <90	Mildly decreased	60 to <90	60 to <90 (CKD 2)
3A	45 to <60	Mildly to moderately decreased	45 to <60	45 to <60 (CKD 3a)
3B	30 to <45	Moderately to severely decreased	30 to <45	30 to <45 (CKD 3b)
4	15 to <30	Severely decreased	15 to <30	15 to <30 (CKD 4)
5	<15	Kidney failure	<15	<15 (CKD 5)

A shift table from baseline to last value on treatment and to minimum value on treatment for eGFR (CKD-EPI)cr will be provided.

7.8.3 Vital signs

Heart rate and blood pressure (diastolic and systolic) over time will be summarised descriptively based on the RS (all data). Descriptive statistics will also be shown graphically.

7.8.4 ECG

Clinically relevant abnormalities found at physical examination will be considered to have already existed prior to signing of informed consent and therefore should be considered baseline conditions instead of adverse events, unless there is good reason to assume that they first appeared after signing of consent.

Outcomes of ECGs will be part of the reporting of medical history or AE reporting. Categorical findings as collected in the eCRF will also be summarised descriptively.

7.8.5 Others

Not applicable.

9. ADDITIONAL SECTIONS

9.1 DERIVATION OF KCCQ DOMAINS

The following algorithm will be used to score the KCCQ.

9.1.1 Kansas City Cardiomyopathy Questionnaire (KCCQ)

There are 10 summary scores within the KCCQ, which are calculated as follows:

1. Physical Limitation

Code responses to each of Questions 1a-f as follows:

- Extremely limited = 1
- Quite a bit limited = 2
- Moderately limited = 3
- Slightly limited = 4
- Not at all limited = 5
- Limited for other reasons or did not do = <missing value>

If at least three of Questions 1a-f are not missing, then the Physical Limitation Score is calculated as follows:

Physical Limitation Score = $100 * [(mean\ of\ Questions\ 1a-f\ actually\ answered) - 1] / 4$

2. Symptom Stability

Code the response to Question 2 as follows:

- Much worse = 1
- Slightly worse = 2
- Not changed = 3
- Slightly better = 4
- Much better = 5
- I've had no symptoms over the last 2 weeks = 3

If Question 2 is not missing, then the Symptom Stability Score is calculated as follows:

Symptom Stability Score = $100 * [(Question\ 2) - 1] / 4$

3. Symptom Frequency

Code responses to Questions 3, 5, 7 and 9 as follows:

Question 3

- Every morning = 1
- 3 or more times a week but not every day = 2
- 1-2 times a week = 3
- Less than once a week = 4
- Never over the past 2 weeks = 5

Questions 5 and 7

- All of the time = 1
- Several times a day = 2
- At least once a day = 3
- 3 or more times a week but not every day = 4
- 1-2 times a week = 5
- Less than once a week = 6
- Never over the past 2 weeks = 7

Question 9

- Every night = 1
- 3 or more times a week but not every day = 2
- 1-2 times a week = 3
- Less than once a week = 4
- Never over the past 2 weeks = 5

If at least two of Questions 3, 5, 7 and 9 are not missing, then the Symptom Frequency Score is calculated as follows:

$$S3 = [(Question 3) - 1]/4$$

$$S5 = [(Question 5) - 1]/6$$

S7 = [(Question 7) – 1]/6

S9 = [(Question 9) – 1]/4

Symptom Frequency Score = 100*(mean of S3, S5, S7 and S9)

4. Symptom Burden

Code responses to each of Questions 4, 6 and 8 as follows:

- Extremely bothersome = 1
- Quite a bit bothersome = 2
- Moderately bothersome = 3
- Slightly bothersome = 4
- Not at all bothersome = 5
- I've had no swelling/fatigue/shortness of breath = 5

If at least one of Questions 4, 6 and 8 is not missing, then the Symptom Burden Score is defined as follows:

Symptom Burden Score = 100*[(mean of Questions 4, 6 and 8 actually answered) – 1]/4

5. Total Symptom Score

The Total Symptom Score is defined as the mean of the following available summary scores:

Symptom Frequency Score and Symptom Burden Score

6. Self-Efficacy

Code responses to Questions 10 and 11 as follows:

Question 10

- Not at all sure = 1
- Not very sure = 2
- Somewhat sure = 3
- Mostly sure = 4
- Completely sure = 5

Question 11

- Do not understand at all = 1
- Do not understand very well = 2
- Somewhat understand = 3
- Mostly understand = 4
- Completely understand = 5

If at least one of Questions 10 and 11 is not missing, then the Self-Efficacy Score is calculated as:

Self-Efficacy Score = $100 * [(\text{mean of Questions 10 and 11 actually answered}) - 1] / 4$

7. Quality of Life

Code responses to Questions 12, 13 and 14 as follows:

Question 12

- It has extremely limited my enjoyment of life = 1
- It has limited my enjoyment of life quite a bit = 2
- It has moderately limited my enjoyment of life = 3
- It has slightly limited my enjoyment of life = 4
- It has not limited my enjoyment of life at all = 5

Question 13

- Not at all satisfied = 1
- Mostly dissatisfied = 2
- Somewhat satisfied = 3
- Mostly satisfied = 4
- Completely satisfied = 5

Question 14

- I felt that way all of the time = 1
- I felt that way most of the time = 2
- I occasionally felt that way = 3

- I rarely felt that way = 4
- I never felt that way = 5

If at least one of Questions 12, 13 and 14 is not missing, then the Quality of Life Score is calculated as:

Quality of Life Score = $100 * [(\text{mean of Questions 12, 13 and 14 actually answered}) - 1] / 4$

8. Social Limitation

Code responses to each of Questions 15a-d as follows:

- Severely limited = 1
- Limited quite a bit = 2
- Moderately limited = 3
- Slightly limited = 4
- Did not limit at all = 5
- Does not apply or did not do for other reasons = <missing value>

If at least two of Questions 15a-d are not missing, then the Social Limitation Score is calculated as:

Social Limitation Score = $100 * [(\text{mean of Questions 15a-d actually answered}) - 1] / 4$

9. Overall Summary Score

The Overall Summary Score is defined as the mean of the following available summary scores:

Physical Limitation Score, Total Symptom Score, Quality of Life Score and Social Limitation Score

10. Clinical Summary Score

The Clinical Summary Score is defined as the mean of the following available summary scores:

Physical Limitation Score and Total Symptom Score

Note: references to “means of questions actually answered” imply the following.

If there are n questions in a scale, and the subject must answer m to score the scale, but the subject answers only n-i, where n-i >= m, calculate the mean of those questions as

(sum of the responses to those n-i questions) / (n-i)

not

(sum of the responses to those n-i questions) / n

The change from baseline to Day 90 in KCCQ-TSS will be calculated as the difference of the score at Day 90 and at baseline.

9.2 ALGORITHM FOR IMPUTATION ACCORDING TO JUMP-TO-PLACEBO METHOD

This algorithm imputes missing on-treatment data as MAR, and then imputes missing off-treatment data as MNAR by a jump-to-placebo method.

The conceptual approach is described by Carpenter et. al. (11). The implementation is planned as follows:

1. Remove any off-treatment data from dataset
2. Non-monotone missing data is imputed under MAR to create a monotone pattern
 - a. 100 imputations are performed by MCMC-MI, stratified by treatment, with the following parameters:
 - i. Baseline value included as a continuous variable, HF status as a binary variable (de novo or decompensated chronic HF)
 - ii. Multiple chains with 200 burn-in iterations per chain
 - iii. Jeffrey's prior
3. SLR-MI is used to impute missing monotone on-treatment data:
 - a. All data is imputed using SLR-MI, separately by treatment, with the following parameters:
 - i. Baseline (continuous), HF status (de novo or decompensated HF) included as covariates
 - ii. All imputed data for patients at an off-treatment time point is deleted
4. On-treatment group means are calculated for each imputation at each visit
 - a. ANCOVA used to calculate adjusted means with the following parameters:
 - i. Baseline (continuous), HF status (de novo or decompensated chronic HF), and treatment included as covariates
 - ii. Restricted Maximum Likelihood and Kenward-Rogers methods
 - iii. Least Square Means used
5. Placebo group on-treatment means at each visit are subtracted from all group on-treatment means at the same visit, to give treatment differences

- a. Note that these will be 0 for the placebo group
6. Individual data is ‘temporarily saved’ at this point, excluding available off-treatment data
7. Treatment differences are subtracted from the respective (by visit and treatment) data values
 - a. Results are the ‘residuals’ after removal of treatment effect(s)
 - b. This is referred to as the residual data
8. Subset of the residual data is created with all patients in placebo group and all patients with missing values at first visit requiring imputation. Note that these missing values will all be off-treatment.
9. Multiple imputation is performed on the first visit requiring imputation
 - a. Linear regression models are used to derive the distributional parameters;
 - i. One imputation per existing imputation
 - ii. Residual subset used
 - iii. Baseline (continuous), HF status (de novo or decompensated chronic HF), all previous visits (continuous) included as model covariates
10. Imputed off-treatment values from subset merged with residual data sets.
11. If visits that require imputation remain, go to step 8, else proceed to next step
12. Original data set, saved data sets and residual data sets are merged so that all missing values in the saved data set are filled with observed off-treatment measurements where available, otherwise the values from corresponding residual data sets are used.
13. The next step depends on the data being imputed:
 - a. For NT-proBNP, the AUC of change from baseline in log-transformed NT-proBNP level will be calculated for these imputed data sets. Then an ANCOVA model will be applied (see [Section 7.5.2](#)).
 - b. For KCCQ-TSS, the stratified win ratio will be calculated using these imputed data sets, by combining with the non-imputed death and HFE data (see [Section 7.4.1](#)). Then take logs of the stratified win ratios.
14. Estimates and variances are combined using Rubin’s rules ([13](#)) to give a single estimate and variance for each parameter of interest across all imputations.

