6.6 HANDLING OF MISSING DATA AND OUTLIERS

6.6.1 Imputation methods

There will be no imputation of data for safety analyses.

For patients who discontinue the trial treatment prematurely, all efforts will be made to follow patients for survival and for any other endpoints including the primary and secondary endpoints until the end of the trial.

Multiple imputations:

Missing data for the Kansas City Cardiomyopathy Questionnaire Total Symptom Score (KCCQ-TSS), as part of the stratified win ratio and NT-proBNP (log-transformed values) will be estimated using multiple imputation, according to whether patients are on-treatment or off-treatment.

Values measured after premature discontinuation of study drug will be included in the analyses. All available on- and off-treatment data up to the planned measurement at Day 90 will be included.

There will be different types of missing data to be considered for the imputation.

Table 6.6.1: 1 Adjusted multiple imputation “jump-to-placebo” approach – the missing data imputation method

Missing data imputation (Assumption of missingness)	Non-monotone	Monotone
On-treatment data	MCMC-MI ¹ (MAR ³)	SLR-MI ² (MAR)
Off-treatment ⁴ data	Jump-to-Placebo (MNAR ⁵)	Jump-to-Placebo (MNAR)

¹ Markov Chain Monte Carlo – Multiple imputation (MCMC-MI)

² Sequential linear regression – Multiple imputation (SLR-MI)

³ Missing at random (MAR)

⁴ Any instance of a patient discontinuing treatment will lead to all future measurements being considered as off-treatment.

⁵ Missing not at random (MNAR)

As the first step, the non-monotone on-treatment missing data will be imputed using Markov Chain Monte Carlo (MCMC) simulation and standard techniques; MI will be performed separately by treatment with baseline value as a continuous variable and HF status as a binary variable (de novo or decompensated chronic HF). One hundred imputations will be performed to ensure adequate efficiency and stability of the estimation for missing data. This step will be referred to as ‘MCMC-MI’.

For the monotone missing on-treatment data, a sequential linear regression MI approach will be used and referred to as ‘SLR-MI’. The MI will be performed on a data set only including on treatment data and once per imputation from the previous step. This procedure will impute values for all missing time points both on- and off-treatment, so imputations for off-treatment values will then be deleted. The regression models will be fitted separately by treatment and

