include the baseline value as a continuous covariate, HF status as a class covariate and the values at previous time points as separate continuous covariates.

To impute the missing off-treatment data, a residual-based approach will be used to enact the 'jump-to-placebo'. Throughout this imputation, all observed off-treatment data will be temporarily removed and added back at the end. A covariate-adjusted difference between the relevant treatment arm and placebo (i.e. 0 for those in the placebo arm) will be calculated at each visit using ANCOVA (with HF status and treatment as categorical covariates and baseline value as a continuous covariate). Next, the relevant estimated treatment difference will be deducted from all observed data in the active treatment groups. Note that the adjustments are for the duration of the imputation only and the original values for the observed data will be in the final imputed data set.

SLR-MI will then be performed once per imputation upon this modified data but only including patients either with missing values and/or those in the placebo arm, ensuring imputations are performed using the placebo distribution. The models will include baseline value as a continuous covariate, HF status as a class covariate and the values at previous time points as separate continuous covariates. All missing data will therefore follow the distribution of the placebo arm, jumping from one arm's distribution to the placebo's at the point of missingness, while still accounting for past within-treatment performance (the residuals). After this imputation, all the original observed values (i.e. off-treatment values) will be restored.

For NT-proBNP, the AUC of change from baseline in log-transformed NT-proBNP level will be calculated using these imputed data sets (imputation performed on the log-transformed data first before AUC values are calculated). Then an ANCOVA model will be applied (see [Section 7.5.2](#)). Rubin's rules ([13](#)) will be used to combine treatment estimates across the 100 imputations. Missing values at Visits 2b and 2c will not be imputed, but observed values at these visits will be used.

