For KCCQ-TSS, the stratified win ratio will be calculated using these imputed data sets, by combining with the non-imputed death and HFE data. Because the stratified win ratio is log-normally distributed ([10](#)), Rubin's rules ([13](#)) can be used on the log-transformed win ratios to combine treatment estimates across the 100 imputations.

The implicit assumption underlying the imputations and analyses is that unobserved off treatment patient measurements will lose any treatment effect immediately post-treatment discontinuation.

A more technical description of the method can be found in [Appendix 9.2](#).

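### SAP Appendix 9.2, step 3, omits the earlier-visit covariates that SAP 6.6.1 specifies for the same imputation step

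*SAP*

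**What the plan says.** SAP 6.6.1 splits missing KCCQ-TSS and log NT-proBNP by treatment status and pattern. Non-monotone on-treatment gaps go to MCMC, and missing off-treatment values go to jump-to-placebo. For the remaining cell it says, before giving the label SLR-MI: "For the monotone missing on-treatment data, a sequential linear regression MI approach will be used and referred to as". Those regressions are fitted by treatment arm. They "include the baseline value as a continuous covariate, HF status as a class covariate and the values at previous time points as separate continuous covariates". The section then points to Appendix 9.2: "A more technical description of the method can be found in".

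Appendix 9.2 presents its numbered list as the planned implementation. Step 3 covers the same SLR-MI step, also by treatment arm, and gives its covariates as "Baseline (continuous), HF status (de novo or decompensated HF) included as covariates". Earlier visits are not mentioned. Step 9, the off-treatment imputation, gives "Baseline (continuous), HF status (de novo or decompensated chronic HF), all previous visits (continuous) included as model covariates".

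Step 13 sends the completed KCCQ-TSS data sets into the stratified win ratio and the completed NT-proBNP data sets into the AUC analysis. Protocol 7.3 leaves the details of the multiple imputation to the SAP, so it does not settle the difference.

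**The concern.** One imputation step feeding the primary analysis has two covariate lists, and the shorter one is in the text a programmer is most likely to code from.

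The step is labelled missing at random. That label is most credible when the model conditions on the observed scores that predict who is missing later. A patient who is worsening at Day 30 and then misses Day 90 while still on treatment should be imputed as someone who was worsening. With baseline and HF status alone, that patient is imputed as an average member of the arm with the same baseline.

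The effect carries forward. Steps 4 and 5 compute group means and treatment differences from data completed in step 3, and step 7 subtracts those differences before the off-treatment imputation. Step 3 values can also serve as earlier-visit covariates in step 9.

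**Working it through.** **1. The texts side by side**

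| Place | Missing data handled | Covariates listed |
|---|---|---|
| 6.6.1, SLR-MI | on-treatment, monotone | baseline, HF status, earlier visits |
| 9.2 step 3 | on-treatment, monotone | baseline, HF status |
| 6.6.1, jump-to-placebo | off-treatment | baseline, HF status, earlier visits |
| 9.2 step 9 | off-treatment | baseline, HF status, earlier visits |

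Rows 1 and 2 describe the same step and differ. Rows 3 and 4 agree.

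**2. Scope of the difference**

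- Non-monotone gaps are filled in step 2: "Non-monotone missing data is imputed under MAR to create a monotone pattern".
- After any treatment discontinuation, later values count as off-treatment (footnote 4 to Table 6.6.1: 1). If missing, they are imputed in steps 8 to 11 with earlier visits included.
- For KCCQ-TSS this leaves patients still on treatment whose last score or scores are missing. Days 15 and 30 are the predictors at risk for Day 90.
- For NT-proBNP the AUC ends at Day 30. The scheduled outpatient predictor at risk is Day 15, plus any observed Visit 2b or 2c values if these enter the model.

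**3. Noise under literal coding**

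Inputs: SD 20 (protocol 7.5). Assumed: correlation b of baseline with each later visit 0.4 to 0.5, and correlation r between later visits 0.6 to 0.75.

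- Baseline only: residual SD = 20 × √(1 − b²). This is 18.3 for b = 0.4 and 17.3 for b = 0.5.
- Adding Days 15 and 30: with p = (r − b²)/(1 − b²), multiply by √(1 − 2p²/(1 + p)).
 - b = 0.4, r = 0.6: p = 0.524, SD 14.7.
 - b = 0.5, r = 0.7: p = 0.600, SD 12.8.
 - b = 0.4, r = 0.75: p = 0.702, SD 11.9.

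The residual SD is therefore about 17 to 18 instead of 12 to 15. Protocol 7.5 calls the 20 baseline-adjusted. Read that way, the comparison is 20 against about 13 to 16 (each value divided by √(1 − b²)).

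**4. Error per imputed Day 90 value**

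This comes from a large-sample simulation with SD 20 and the correlations above. HF status was left out of both models. Missingness depended on Day 30, so that patients missing Day 90 were about 12 points lower there.

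| b, r | Missing | Day 30 gap | Baseline only | With earlier visits | Arm-mean shift, baseline only |
|---|---|---|---|---|---|
| 0.5, 0.7 | 5% | −11.8 | +5.04 | −0.26 | +0.25 |
| 0.5, 0.7 | 15% | −11.4 | +5.19 | −0.06 | +0.78 |
| 0.4, 0.75 | 5% | −12.0 | +7.30 | −0.11 | +0.36 |
| 0.4, 0.75 | 15% | −11.5 | +6.73 | −0.10 | +1.01 |

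When missingness is unrelated to Day 30, the baseline-only error is also about zero. The cost is then noise only.

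**5. Bias in the treatment contrast**

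Bias = difference in missing share × Day 30 gap × slope of Day 90 on Day 30. Assumed: shares differing by 2 to 5 percentage points, a gap of 5 to 10 points and a slope of 0.5 to 0.7, with the same gap and slope in both arms.

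- Low: 0.02 × 5 × 0.5 = 0.05 points, and 0.05/6 = 0.8% of the planned effect of 6.
- High: 0.05 × 10 × 0.7 = 0.35 points, and 0.35/6 = 5.8%.

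The gap should be net of baseline, because step 3 keeps baseline; a raw gap overstates the bias a little. In the simulation the error per raw gap point was 5.04/11.8 = 0.427 to 7.30/12.0 = 0.608. These ratios give 0.02 × 5 × 0.427 = 0.04 to 0.05 × 10 × 0.608 = 0.30, the same order.

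Equal missing shares cancel only if the gap is also alike. With 10% missing in both arms, gaps differing by 5 points and a slope of 0.6, the bias would be 0.10 × 5 × 0.6 = 0.30.

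**The case against.** The strongest reply is that there is only one intended model and 6.6.1 states it. Step 3 calls its method SLR-MI, a term 6.6.1 introduces as sequential linear regression and twice specifies with earlier visits. The appendix is offered as a technical description of that method, not a change to it. Step 2.a.i also lists only baseline and HF status for the MCMC step, although that step fills holes in the visit series and must involve the visits. Steps 2 and 3 may simply list the extra covariates and take the visits as understood. Step 9 says linear regression inside a visit-by-visit loop, so it has to spell its covariates out.

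This stands as an argument about intent. A reader might infer from the contrast between steps 3 and 9 that the SAP deliberately ignores Day 15 and Day 30 scores. The documents do not support that: step 3 does not call its list exhaustive, and nothing in the SAP says earlier values are dropped.

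The limits on scope and size also stand. Many deteriorating patients will have stopped treatment and so fall outside step 3. Pairs decided on death or HFEs never reach KCCQ-TSS.

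The reply does not remove the inconsistency. Two operative texts give different lists for one step, none is said to prevail, and step 9 shows that the appendix names earlier visits elsewhere.

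**Conclusion.** The point holds as a low-severity inconsistency, probably a drafting omission. It matters only if step 3 is coded literally. In that case the Day 15 and Day 30 scores are lost as predictors of monotone-missing on-treatment Day 90 KCCQ-TSS, and Day 15 is lost as a predictor of Day 30 NT-proBNP.

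The firmer consequences are a weaker missing-at-random assumption and noisier imputations. Bias in the mean KCCQ-TSS contrast is likely small, about 0.05 to 0.35 points. It is near zero if missingness is similar in both arms, in amount and in its relation to earlier scores, or is unrelated to those scores. The gaps, slopes, correlations and missing shares are all assumptions. No direction of bias is established, and the effect on the win ratio itself was not calculated. A reader might infer that the primary result is materially biased; these figures do not show that.

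**What to change.** In Appendix 9.2, step 3.a.i, add after HF status: *plus the value at each earlier visit, entered as a continuous covariate*. Restore the word *chronic* to the HF status label so that it matches the other steps. Step 3 then agrees with 6.6.1, "and the values at previous time points as separate continuous covariates", and with step 9, "all previous visits (continuous) included as model covariates".

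The cost is one phrase in the SAP and a check that the imputation program uses the longer list. It changes no stated intention, data collection or sample size. It should be done before unblinding, so that the choice between the two lists is not made with results in view.
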